3.1 General Description

This is a Phase 2, proof-of-concept, multicenter, randomized, double-blind, placebo-controlled study to evaluate the efficacy and safety of lirentelimab in adult subjects with moderate-to-severe H1-AH refractory CSU. Subjects enrolled in the study will receive 6 doses of 300 mg lirentelimab SC or placebo SC administered every 2 weeks, followed by the option to enroll in the open-label extension (OLE) period, contingent on defined selection criteria, to receive 6 doses of 300 mg lirentelimab SC. Subjects will be observed for a post-treatment period of 12 weeks.

Based on the feedback from chronic spontaneous urticaria experts and completed feasibility assessments, it is expected that each site will be able to screen three subjects and enroll two of them during the duration of the enrollment period. Enrollment is considered to be competitive. To ensure the enrollment goal is achieved in a timely manner, up to 70 sites (approximately 55 in the US, and 15 in Germany and Poland) will be initiated. If study enrollment goal can be achieved with fewer sites and meet the study timeline, then fewer sites may be needed.

Subjects will be consented and then screened for up to 3 weeks. Subjects who have been on a stable, approved dose regimen of H1-AH prior to screening will undergo a 2-week eligibility screening period. Subjects who are not on a stable approved H1-AH dose regimen will be allowed an additional 1 week during the screening period during which they must reach a stable approved dosing regimen before entering the 2-week eligibility screening period.

Stable approved doses of H1-AH for study purposes is defined as an H1-AH regimen between 1x and 4x of the licensed dose and at the licensed frequency of dosing for the treatment of CSU, for at least 1 week prior to screening.

Baseline H1-AH dosing regimen must be established by Day -14 (14 days prior to randomization) for purposes of the screening eligibility period. Baseline disease activity data will be collected with daily assessment of itch and hives severity, both of which will be used to calculate a weekly UAS7. Subjects who meet eligibility criteria at both Day -7 and Day 1 can be enrolled in the study.

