4.2.6 Summary Measure of the Estimand

Least squares mean (LSM) (and standard error [SE]) of change from baseline in UAS7 to Week 12 and the between treatment difference in the lirentelimab SC and placebo SC groups LSM.

5. Statistical Methods

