5.10 Examination of Subgroups

Key endpoints will be summarized by subgroup to assess the consistency of the treatment effect across each of these subgroups. For any subgroup, if there are zero subjects within a stratification

stratum in any treatment group, the statistical model will not be adjusted by the stratification factors. Subgroups to be considered are:

- Sex (Male, Female)
- Age group ($<65, \geq 65$)
- Race (White, Non-White)
- Ethnicity (Hispanic or Latino, Not Hispanic or Latino)
- Region (U.S., non-U.S.)
- Baseline weekly itch severity score $(<13, \ge 13)$
- History of angioedema at screening (Yes, No)
- Prior omalizumab experience for the treatment of CSU (exposed, naïve)
- Baseline UAS7 score (16–27, 28–42)
- Duration of disease prior to baseline (<2, 2-10, >10 years)
- Screening IgE (\geq 43 kU/L, <43 kU/L)

6. Statistical Analysis

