6.9.1 Analysis of Primary Efficacy Endpoint

The primary endpoint will be analyzed using analysis of covariance (ANCOVA) using the imputed data set described below. The synthesizing method will be used to combine the results from multiple imputations. The least square (LS) mean, standard error (SE), and 95% confidence interval (CI) for each treatment group and for the between group difference will be derived from the ANCOVA model

with treatment as factor, and baseline UAS7 score and omalizumab experience for the treatment of CSU (exposed, naïve) as covariates. The hypothesis test for the treatment effect will be carried out by the F-test.

For the analysis described above, missing data from subjects who prematurely discontinue the randomized treatment, initiate any treatment adjustments as outlined in Section 4.2.5 (e.g., use of prohibited or rescue medication), or missing daily PRO scores as described in Section 2.1 will be imputed using multiple imputation (MI) techniques. There are five steps in the MI process.

- 1) Check missing data patterns.
- 2) Impute non-monotonic or intermittent data until only monotone missing data remains.
- 3) Use monotone regression to impute monotone missing data and create multiply imputed data sets.
- 4) Run the primary efficacy analysis (ANCOVA using SAS PROC MIXED) on the multiply imputed data sets.
- 5) Use SAS PROC MIANALYZE to combine the efficacy output to get a single estimate from all the imputed data sets.

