6.9.1.1 Step 1. Checking missing data patterns

For this study, the missing data patterns will be checked by treatment and visits (baseline to Week 12). There are 3 steps to this process:

Create dataset for efficacy measure including visits from baseline to Week 12

```
data mi_chk1; set datax;
where paramcd="UAS7" and baseline <= visit <=Week 12;
run;
```

Transpose dataset to display each visit as one column:

```
proc sort data = mi_chk1; by treatment id;
proc transpose data=mi_chk1 out=mi_chk2 prefix='';
by treatment id;
id avisitn;
var aval;
run;
```

Use PROC MI with the NIMPUTE=0 option to create the "Missing Data Patterns" table for the specified variables:

```
ods output MissPattern=missp;
proc mi data=mi_chk2 NIMPUTE=0;
```

by treatment; var visit0(i.e., baseline) – visit12 (i.e., Week 12); run;

6.9.1.2 Step 2. Impute non-monotonic/intermittent data until only monotone missing data remains.

Fill in the intermittent missing data using the following code.

```
proc sort data = mi_chk2; by treatment;
proc mi data=mi_chk2 seed=12345 NIMPUTE=50 out=MI;
  by treatment;
  mcmc impute=monotone;
  var Visit0 – Visit12;
  run;
```

6.9.1.3 Step 3. Use monotone regression to impute monotone missing data and create multiply imputed data sets.

```
proc sort data = mi; by _Imputation_;
proc mi data=mi out=mi_reg seed=54321 nimpute=1;
by _Imputation_;
var treatment Visit0 - Visit12;
class treatment;
monotone regression;
run;
```

6.9.1.4 Step 4. Run the efficacy analyses (PROC MIXED) on the multiply imputed data sets.

```
/** Recalculate change from baseline at Week 12**/
data UAS7 imputed;
 set mi reg;
 chg=Visit12-Visit0;
run;
proc sort data=UAS7 imputed out=UAS7 imputed1;
 by imputation ;
run;
/** ANCOVA by imputation **/
ods output diffs=diffs lsmeans=lsm;
proc mixed data=UAS7 imputed1 method=reml;
 by imputation ;
 class region omalizumab experience TREATMENT;
 model CHG= region omalizumab experience Visit0 TREATTMENT;
 lsmeans TREATMENT / diff;
quit;
```

ods output close;

6.9.1.5 Step 5. Combine estimates of the 50 PROC MIXED models to create an overall estimate and a relative efficacy score.

```
/** Combine LS Means (by treatment and difference) **/
data lsmdiff;
  set lsm diffs(in=d);
  if d then treattment='DIFF';
run;
proc sort;by TREATMENT;run;
/** Synthesized results **/
ods output ParameterEstimates=SYNDIF;
proc mianalyze data=LSMDIFF alpha=0.05;
  by TREATMENT;
  modeleffects ESTIMATE;
  stderr stderr;
run ;
ods output close;
```

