proc mixed data=CONTINUOS method=reml; class TREATMENT USUBJID AVISITN REGION USA7_SCORE (16–27, 28–42) OMALIZUMAB_EXPERIENCE; model CHANGE= BASELINE_OF_OUTCOME USA7_SCORE (16–27, 28–42) OMALIZUMAB_EXPERIENCE TREATMENT AVISITN REGION TREATMENT*AVISITN BASELINE_OF_OUTCOME *AVISITN / DDFM=KR; REPEATED AVISITN / SUBJECT=USUBJID (TREATMENT) TYPE=UN; RANDOM REGION; LSMEANS TREATMENT*AVISITN / PDIFF CL; RUN;

Where TREATMENT = planned treatment group in numeric (1 = placebo SC, 2 = lirentelimab SC); AVISITN = time point in Weeks.

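### As coded, the arm-level LS means weight region and omalizumab experience 50:50 rather than at the enrolled mix; the treatment difference is unaffected, and the fix is one option

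*SAP*

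**What the plan says.** SAP 4.2.6 makes the arm-level result part of the estimand's summary measure: "Least squares mean (LSM) (and standard error [SE]) of change from baseline in UAS7 to Week 12", together with the between-arm difference. SAP 6.9.1 accordingly asks for an LS mean, SE and 95% CI for each arm as well as for the difference. The model it describes has treatment as the factor, with "baseline UAS7 score and omalizumab experience for the treatment of CSU (exposed, naïve) as covariates". Region is not in that description, nor in protocol 16.6.1.

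The code in SAP 6.9.1.4 (Step 4) is different. It has "class region omalizumab experience TREATMENT", then "model CHG= region omalizumab experience Visit0 TREATTMENT", then "lsmeans TREATMENT / diff". The MMRM code in SAP 6.9.2 has region, omalizumab experience and the UAS7 stratum as class factors and requests "LSMEANS TREATMENT*AVISITN / PDIFF CL". Neither statement carries a weighting option, and the SAP text names no weights.

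On the expected mix, SAP 3.1 says "up to 70 sites (approximately 55 in the US, and 15 in Germany and Poland) will be initiated", with two enrolled subjects expected per site and competitive enrolment. SAP 5.10 gives region two levels (U.S. and non-U.S.), although the MMRM text in 6.9.2 speaks of country. Neither document states an expected share, cap or quota for omalizumab-exposed subjects.

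**The concern.** By SAS default, an LS mean gives equal weight to every level of the other class factors. As coded, each arm's mean change is therefore the model's prediction for a group that is half U.S. and half non-U.S., and half exposed and half naïve. The MMRM adds half in each UAS7 stratum. The enrolled group is expected to look different, at least by region.

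Two things follow for the arm-level results. Their intervals are wider than the data require, because a small subgroup is weighted up to one half. Their point estimates move if the factor predicts change once baseline UAS7 is in the model. At stake are the reported arm-level changes and their 95% CIs. These are prespecified primary outputs, and they bear most directly on the estimand's question of what improvement a subject could expect at 12 weeks.

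**Working it through.** **Plan's own figure first.** Difference 8, SD 11, 55 per arm, two-sided 0.05: SE = 11 × √(2/55) = 2.098, and 8/2.098 − 1.96 = 1.85, so power is about 96.8%. The stated figure of more than 90% is reproduced. The plan gives no figure for LS-mean weights.

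**Inputs.** SD 11 (SAP 3.4); 65 per arm (SAP 3.2); non-US share 15/70 = 0.214, from the site counts in SAP 3.1 and assuming sites enrol equally. The omalizumab-exposed share p is not in the documents, so 10% to 30% is assumed. The factors are taken as independent of each other, of arm and of baseline, and between-imputation variance is ignored.

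**Arm-level variance.** At observed margins, Var = SD²/n = 121/65 = 1.862, so SE = 1.364. Each two-level factor is estimated from both arms (2n subjects) with variance SD²/[2n·p(1−p)], and equal weighting moves the arm mean by (0.5 − p) times its coefficient. Hence:

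Var(equal) = (SD²/n) × {1 + ½ Σ (0.5 − p)²/[p(1 − p)]}

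- Region, p = 0.214: 0.0816/0.1684 = 0.485
- Exposed, p = 0.30: 0.04/0.21 = 0.190
- Exposed, p = 0.20: 0.09/0.16 = 0.5625
- Exposed, p = 0.10: 0.16/0.09 = 1.778

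| Model and mix | Multiplier in braces | SE | Excess over 1.364 | 95% half-width |
|---|---|---|---|---|
| Observed margins | 1 | 1.364 | – | 2.67 |
| Region imbalance only (50% exposed) | 1.242 | 1.521 | 11% | 2.98 |
| Region, 30% exposed | 1.338 | 1.578 | 16% | 3.09 |
| Region, 20% exposed | 1.524 | 1.684 | 23% | 3.30 |
| Region, 10% exposed | 2.131 | 1.992 | 46% | 3.90 |
| No region, 30% exposed | 1.095 | 1.43 | 5% | 2.80 |
| No region, 20% exposed | 1.281 | 1.54 | 13% | 3.03 |
| No region, 10% exposed | 1.889 | 1.88 | 37% | 3.68 |

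The percentages do not depend on n or SD. If region were coded as three countries with the non-US subjects split evenly (assumed), the excess from region alone would be about 27%.

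**Shift in the arm means.** Shift = (0.5 − share) × effect of the factor given baseline. For region that is 0.286 points per point of effect. For omalizumab it is 0.2, 0.3 or 0.4 points per point at 30%, 20% or 10% exposed. The documents do not give these effects. At 20% exposed, assumed omalizumab effects of 2, 4 and 8 points would give shifts of 0.6, 1.2 and 2.4 points.

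**Between-arm difference.** The Step 4 model has no treatment interaction, so both arms move by the same amount and the shift cancels. The SE of the difference is 11 × √(2/65) = 1.930 under either weighting. One simulated data set gave a difference of −7.348 with SE 1.831 both ways.

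**MMRM.** The same mechanism applies, with a 50:50 weighting of the UAS7 stratum as well. It is not quantified here because the documents give no expected stratum split.

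**The case against.** The strongest reply is that no inference changes. The hypothesis test, the error control and the sample size all concern the difference between arms, which is identical under either weighting. That stands, and it limits the severity.

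A reader might infer that the code describes a population the trial does not enrol. The documents do not support this. SAP 4.2.1 defines the population by the entry criteria, and those set no regional or omalizumab mix. A 50:50 mix consists of eligible subjects, and an LS mean is what 4.2.6 asks for. The case for observed margins is relevance to the enrolled group and precision, not that equal weights breach the estimand. Nor do the documents say that the arm means will support labelling; this is a Phase 2 proof-of-concept trial.

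The printed code is also schematic. `TREATTMENT` in the MODEL statement does not match the CLASS statement, and the transposed data set from Step 1 carries neither region nor omalizumab status. The prose calls omalizumab experience a covariate. If it were entered as a 0/1 variable outside CLASS, its LS mean would already be taken at the sample share. All this is fair, but the code is the only place where the SAP indicates the weighting.

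The sizes rest partly on assumptions. The 21% non-US share is a ratio of sites under competitive enrolment, and the exposed share is not documented. A material shift in the point estimates is not established. In the earlier open-label study (protocol 2.3), mean UAS7 changes were −13.9 in omalizumab-naïve and −14.0 in omalizumab-failure subjects. At 20% exposed, that 0.1-point gap gives a shift of only 0.3 × 0.1 = 0.03 points. Those changes are unadjusted, however. The percentage changes imply baselines near 19 (13.9/0.732) and 30 (14.0/0.466), so an effect given baseline cannot be excluded. That failure cohort also differs from the exposed subjects here, because protocol 8.5 excludes primary non-responders.

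**Conclusion.** The point holds as a cheap improvement of low severity. As coded, the arm-level LS means are taken at a 50:50 mix that the plan neither states nor expects. With SD 11, 65 per arm and equal enrolment by site, the arm-level SE is about 1.52 instead of 1.36 from region alone. It is about 1.58 to 1.99 if 30% to 10% are exposed (assumed range). If the prose model without region governs, the excess rests on omalizumab alone: 5% to 37% over the same range. Any shift in the arm means depends on prognostic effects whose size is unknown and may be small.

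It would be wrong to conclude that the primary comparison is biased or loses power. The treatment difference, its CI, the p-value and the power are unaffected. The mismatch between prose and code on region is a definite inconsistency and should be settled in any case.

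**What to change.** Add observed-margin weights (the OM option, based on the mITT baseline data) to the LSMEANS statement in SAP 6.9.1.4 and to the one in the 6.9.2 MMRM. Use the same baseline mix for every week in the MMRM, so that missing visits do not alter the weights. Use one set of margins for both arms (no BYLEVEL option), so that the difference stays as it is. Say in the text of 6.9.1 which weights are used. If the sponsor prefers 50:50, say so there instead.

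At the same time, reconcile whether region is in the primary model (prose against Step 4 code), and whether the MMRM uses region or country.

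The cost is one option in two procedure calls and a sentence of text; SAP 5.1 allows such a change, documented, before database lock. The downside is that arm means are no longer at a 50:50 mix for comparison with studies reported that way.

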6.9.2 Analysis of Secondary and Exploratory Efficacy Endpoints

The binary secondary and exploratory efficacy endpoints will be analyzed using the Cochran-Mantel-Haenszel test adjusted by omalizumab experience for the treatment of CSU (exposed, naïve), UAS7 score (16–27, 28–42), and region (U.S., non-U.S.) at Week 12. A sample SAS code is as follows:

```
* COMPUTES CMH P-VALUE AND NEWCOMBE COMMON RISK DIFFERENCE ;
ods output CMH=PVAL(where=(althypothesis='Row Mean Scores Differ'))
CommonPdiff=DIFF;
proc freq data=ADEF ;
      tables UAS7*OMALIZUMAB_EXPERIENCE*REGION*TRTP*RESP / cmh(MF)
commonriskdiff
(cl=NEWCOMBE) ;
run ;
```

The Mantel-Fleiss (MF) criterion will be performed, and if it is not met while using the option CMH (MF) in SAS procedure PROC FREQ, analyses including each factor separately in CMH test will be conducted. Should assumption per the MF criterion not be satisfied, the comparison will be based on a Fisher's exact test after collapsing across levels of the stratification factor and country.

Below is an example of the SAS code for the Fisher's exact test:

```
* COMPUTE 95% EXACT CONFIDENCE INTERVAL FOR %RESPONSE FOR INDIVIDUAL
TREATMENT ;
ods output BinomialCLs=CL ;
proc freq data=ADEF ;
    table RESP / out=CNTS bin(cl=midp) ;
    by TRTP ;
run;
* COMPUTE 95% EXACT CONFIDENCE INTERVAL AND FISHERS EXACT P-VALUE FOR
BETWEEN TREATMENT DIFFERENCE ;
ods output FishersExact=PVAL(where=(name1='XP2_FISH'))
RiskDiffCol2=DIFF(where=(row='Difference') ;
proc freq data=ADEF ;
    table TRTP*RESP / riskdiff(cl=exact) exact ;
run ;
```

For the analysis described above, missing data from subjects who prematurely discontinue the randomized treatment, initiate any treatment adjustments as outlined in Section 4.2.5 (e.g., use of prohibited or rescue medication), or missing daily PRO scores as described in Section 2.1 will be imputed using non-response imputation.

To assess the impact of the above "non-responder" rule, the missing data strategy will employ mixed model for repeated measures (MMRM) technique. This approach assumes missing observations are missing at random and borrows information from subjects in the same treatment group considering the missingness of data through the correlation of the repeated measurements. The SAS procedure PROC GLIMMIX will be used for this purpose. The model will include treatment, region, omalizumab experience for the treatment of CSU (exposed, naïve), UAS7 score (16–27, 28–42), visit, and treatment-by-visit-interaction as fixed categorical effects, and baseline and baseline-by-visit-interaction as fixed categorical effects, standard error, two-sided 95% confidence interval for odds ratio and p-values at time points of interest.

All secondary and exploratory efficacy endpoints of continuous nature will utilize MMRM procedure after applying the primary censoring rule, i.e., the rule will censor data after permanent study drug discontinuation or after rescue therapy that applies the censoring rule as described in Section 4.2.5. This censoring rule is equivalent to using all the data up to discontinuation or rescue.

The MMRM model will include fixed effects for baseline value, omalizumab experience for the treatment of CSU (exposed, naïve), UAS7 score (16–27, 28–42), country, treatment, study week, the treatment-by-week interaction, and the baseline-by-week interaction and allow for random subject effects. Treatment and week will each be fitted as categorical variables. The model will assume unstructured covariance structure. If the model with unstructured covariance does not converge, then other covariance structures will be considered to model the within-subject errors. The Kenward-Allakos Inc. Page 36 of 49 *Confidential*

Rogers approach for computing denominator degrees of freedom will be used to account appropriately for pooling of within-subject and between-subject variance estimates. The LS and 95% CI for the difference between groups will be estimated using the simple contrast at each time point. Below is an example of the SAS code for the MMRM:

proc mixed data=CONTINUOS method=reml; class TREATMENT USUBJID AVISITN REGION USA7_SCORE (16–27, 28–42) OMALIZUMAB_EXPERIENCE; model CHANGE= BASELINE_OF_OUTCOME USA7_SCORE (16–27, 28–42) OMALIZUMAB_EXPERIENCE TREATMENT AVISITN REGION TREATMENT*AVISITN BASELINE_OF_OUTCOME *AVISITN / DDFM=KR; REPEATED AVISITN / SUBJECT=USUBJID (TREATMENT) TYPE=UN; RANDOM REGION; LSMEANS TREATMENT*AVISITN / PDIFF CL; RUN;

Where TREATMENT = planned treatment group in numeric (1 = placebo SC, 2 = lirentelimab SC); AVISITN = time point in Weeks.

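### The SAP 6.9.2 sample code for binary endpoints reads different response levels in different calls, so one output would describe non-response and the difference would change sign between the CMH and Fisher branches

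*SAP*

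**What the plan says.** SAP 6.9.2 covers all binary secondary and exploratory efficacy endpoints. The third secondary endpoint in SAP 2.2, the proportion with UAS7 = 0 at Week 12, is one of them. The section gives sample code for two branches.

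- **CMH branch.** The table request is "tables UAS7*OMALIZUMAB_EXPERIENCE*REGION*TRTP*RESP / cmh(MF"), with COMMONRISKDIFF asking for Newcombe limits and no COLUMN= option. The result is saved through "CommonPdiff=DIFF".
- **Fisher branch, per-arm interval.** The comment begins "COMPUTE 95% EXACT CONFIDENCE INTERVAL FOR %RESPONSE FOR INDIVIDUAL". The call is "table RESP / out=CNTS bin(cl=midp"), run by TRTP, with no LEVEL= option.
- **Fisher branch, difference.** The call is "table TRTP*RESP / riskdiff(cl=exact) exact", and the output kept is "RiskDiffCol2=DIFF(where=(row='Difference"), that is, column 2.

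On moving between branches the SAP says: "Should assumption per the MF criterion not be satisfied, the comparison will be based on a Fisher's exact test". An intermediate step, with each factor entered separately in a CMH test, comes before that.

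The SAP does not say how RESP or TRTP is coded, sets no ORDER= option and does not give the direction of the difference. The only treatment coding in 6.9.2 belongs to the MMRM variable TREATMENT: "planned treatment group in numeric (1 = placebo SC, 2 = lirentelimab SC").

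**The concern.** A reader of the output needs the per-arm percentages and the difference to refer to the same outcome, and the difference to have one direction. Here one call names the second response level and the other two leave the level to the software. If the software default is the first level, the calls cannot all refer to responders.

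At stake is how the effect on UAS7 = 0 is described: either per-arm intervals labelled as response that belong to non-response, or a difference that belongs to non-response. The difference would also change direction according to a data-dependent check (Mantel-Fleiss). Both branches save it under the same dataset name, DIFF, so nothing in the output name would show which convention applied.

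**Working it through.** **Inputs**

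- From SAP 6.9.2: the three calls above, all with RESP as the column variable or the only variable, and TRTP as rows in the two-way tables.
- From SAP 3.2: about 65 subjects per arm.
- Assumed: PROC FREQ defaults. BINOMIAL without LEVEL= reports the first level, COMMONRISKDIFF without COLUMN= uses column 1, and a risk difference is row 1 minus row 2. The SAP does not state these, and SAS was not run.
- Assumed, because the SAP gives no UAS7 = 0 rates: 13/65 responders on lirentelimab and 7/65 on placebo.

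**Step 1: which outcome each call describes**

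No ORDER= is set, so the calls share one ordering of RESP.

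| Call | Level used | If response is level 2 | If response is level 1 |
|---|---|---|---|
| Per-arm interval | 1 (default) | non-response | response |
| CMH difference | 1 (default) | non-response | response |
| Fisher difference | 2 (explicit) | response | non-response |

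Neither coding makes all three rows say response.

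**Step 2: sign of the difference**

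For rows A and B and a two-level outcome, column 1 gives (1 − pA) − (1 − pB) = −(pA − pB) when response is column 2. That is the exact negative of column 2. The Mantel-Haenszel common difference is a weighted sum of such terms with weights nA·nB/(nA + nB), which do not depend on the column, so it changes sign too.

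Take rows as 1 = placebo and 2 = lirentelimab (borrowing the MMRM coding) and response as level 2:

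- Column 1: 58/65 − 52/65 = 89.2% − 80.0% = +9.2 points (non-response).
- Column 2: 7/65 − 13/65 = 10.8% − 20.0% = −9.2 points (response).

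Making response level 1, or putting lirentelimab in row 1, reverses both signs. The two columns remain opposite. These are crude differences; a stratified estimate would generally differ somewhat in size.

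A made-up four-stratum example (placebo versus lirentelimab responders 2/20 v 7/20, 3/25 v 9/25, 1/12 v 3/12, 0/8 v 1/8) gave a common difference of +0.215 on one column and −0.215 on the other.

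**Step 3: per-arm intervals**

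Mid-p 95% limits for x out of n: the lower limit solves P(X > x) + ½P(X = x) = 0.025, and the upper limit solves P(X < x) + ½P(X = x) = 0.025.

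| Arm | Responders, interval intended | First-level interval if response is level 2 |
|---|---|---|
| Lirentelimab | 13/65: 11.6–31.0% | 52/65: 69.0–88.4% |
| Placebo | 7/65: 4.8–20.1% | 58/65: 79.9–95.2% |

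**Step 4: tests**

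Two-sided Fisher p for 13/65 versus 7/65 is 0.224 whichever column is called response. In the four-stratum example the CMH p was 0.0022 for either column.

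**Step 5: the label**

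The per-arm comment says exact, but the option requests mid-p limits. For 13/65 the exact (Clopper-Pearson) interval is 11.1–31.8%, against 11.6–31.0% for mid-p.

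**The case against.** The best case for the plan has four parts.

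- **The code is a sketch.** The SAP calls it a sample and an example, and the surrounding code has obvious slips (misspelt variable names, for instance), so a programmer will rewrite it. The endpoint itself is clear from the prose and the table titles. This stands: the error reaches the outputs only if the code is programmed as printed.
- **Two of the three legs are software defaults.** Only the second-column selection is explicit in the SAP. This also stands as a stated assumption. Given those defaults, the mismatch follows under every coding of RESP.
- **No inference changes.** A reader might infer that the hierarchical test of UAS7 = 0 is compromised. It is not. The sequence in SAP 5.9 uses p-values, and the two-sided CMH and Fisher p-values do not depend on which column is called response.
- **Validation would catch it.** SAP section 7 requires independent reprogramming and a consistency check of the whole output set. A reader might infer that two programmers working from the same code would agree on the error and pass it. That is possible but speculative: a 20.0% response rate beside an interval of 69.0–88.4% would be noticed readily. A difference with the wrong sign convention is less conspicuous.

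A reader might also take the mid-p choice as a coverage defect. The figures do not support that. At n = 65, mid-p coverage is 93.8% at a true rate of 10% and 94.3% at 30%, but 95.8% at 20% and 95.6% at 25%. Mid-p is a reasonable choice; only the label is wrong.

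**Conclusion.** The point holds as a minor error in the sample code. As printed, and under the PROC FREQ defaults, either the per-arm intervals and the CMH difference or the Fisher difference describe non-response, and the two branches use opposite sign conventions.

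That conclusion does not depend on the coding of RESP or TRTP. Which output is wrong does depend on RESP, and the particular signs depend on both codings, neither of which the SAP states. In particular, the 69.0–88.4% and 79.9–95.2% intervals arise only if response is the second level. If it is the first, the per-arm intervals are correct and the Fisher difference is the one that describes non-response.

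The effect is confined to estimates, intervals and their direction.

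**What to change.** Amend SAP 6.9.2 before unblinding:

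1. State the coding of RESP, with level 2 = responder, and the coding and row order of TRTP.
2. Add LEVEL= for the response level to the binomial request.
3. Add COLUMN=2 to COMMONRISKDIFF.
4. Keep RiskDiffCol2 in the Fisher branch.
5. State that the difference is lirentelimab minus placebo in both branches. Because the contrast is row 1 minus row 2, lirentelimab must be the first row of TRTP, or the sign must be reversed on output.
6. In the per-arm comment, replace the word for exact with mid-p. Switching to exact limits is optional and would widen the intervals slightly (11.1–31.8% instead of 11.6–31.0% for 13/65).

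The cost is two added options, a sentence or two on coding and direction, and one changed word. Data collection, design, sample size and testing stay as they are.

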16.6 Efficacy Analysis

16.6.1 Primary Efficacy Endpoint Analysis

The primary endpoint will be analyzed by analysis of covariance (ANCOVA). The least square (LS) mean, standard error (SE), and 95% CI for each treatment group and for the between group difference will be derived from ANCOVA with treatment as a factor, baseline UAS7 (continuous), and omalizumab experience for the treatment of CSU (exposed vs. naïve) as covariates. Data on subjects who experience an ICE (i.e., exit the study prematurely or initiate prohibited or rescue medications) prior to the end of Week 12 will be set to missing. Missing data imputation method will be provided in the SAP.

Handling of missing PRO data for less than four data entries per week, other than during Screening, will be addressed in SAP.

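### The model meant to test the non-responder rule for UAS7 = 0 enters baseline as a categorical effect, which over-parameterises it and biases its odds ratio

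*SAP*

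**What the plan says.** In SAP 6.9.2, binary endpoints are tested by CMH, with discontinuation, rescue or prohibited medication and missing diary weeks scored as non-response. A repeated-measures model is then planned to assess the impact of that rule: "The SAS procedure PROC GLIMMIX will be used for this purpose".

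The model sentence has two lists. The first contains treatment, region, omalizumab experience, the UAS7 stratum (16–27, 28–42), visit and treatment-by-visit, all categorical. The second is for baseline, also as categorical: "baseline and baseline-by-visit-interaction as fixed categorical effects". It then runs straight into output statistics without a verb. No code, link, covariance structure, visit list or convergence fallback is given for this model.

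Elsewhere baseline is continuous:
- Protocol 16.6.1, primary ANCOVA: "baseline UAS7 (continuous), and omalizumab experience for the treatment of CSU (exposed vs. naïve) as covariates".
- SAP 6.9.1.4, primary analysis code: the baseline variable is in the MODEL statement but not in CLASS.
- SAP 6.9.2, MMRM for continuous endpoints: "Treatment and week will each be fitted as categorical variables". Baseline is not named there, and the sample code's list, "class TREATMENT USUBJID AVISITN REGION USA7_SCORE (16–27, 28–42) OMALIZUMAB_EXPERIENCE", omits it.

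**The concern.** UAS7 = 0 is the third secondary endpoint in the fixed testing sequence (SAP 2.2 and 5.9). Its result depends on counting every dropout, rescued subject and missing Week 12 as a failure. The GLIMMIX model is the only analysis aimed at that rule. A per-protocol analysis of UAS7 = 0 is also planned (SAP Appendix 2, Table 14.2.2.3b), but it changes the population and leaves the imputation rule in place.

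A score with 27 or more values, entered as categories and crossed with visit, leaves only a handful of subjects per level. Many levels will hold no responders, or only responders, so their coefficients diverge. In logistic models such sparse nuisance terms push the treatment odds ratio away from 1. A gap between this model and the CMH result could then come from the imputation rule or from the coding, and a reader could not tell which.

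**Working it through.** **Inputs from the documents.** Entry requires UAS7 of at least 16 on a 0–42 scale (protocol 8.4). About 130 subjects are randomized 1:1 (SAP 3.2), and the sample size is based on 55 per group (SAP 3.4). Weeks with at least 4 scored days are prorated (SAP 2.1.1). There are 7 scheduled post-baseline visits to Week 12 (Days 8, 15, 29, 43, 57, 71, 85; SAP Table 6), or 12 weekly diary scores. The SAP does not say which set the model uses.

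**The plan's own figure.** The documents give no number for this model. The one design figure, over 90% power with 55 per group (difference 8, SD 11, two-sided 0.05), reproduces at 96.8%. The present point does not depend on it.

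**Levels of baseline.** 42 − 16 + 1 = 27 integer values. Prorating over 4 to 7 days gives up to 68 distinct values of at least 16. With 27 levels there are 110/27 = 4.1 to 130/27 = 4.8 subjects per level.

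**Parameters for baseline and baseline-by-visit, T time points.**
- Continuous: 1 + (T − 1) = T, so 7 or 12.
- Categorical: 26 + 26(T − 1) = 26T, so 182 or 312.

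**Whole model.** Intercept, treatment, region, omalizumab experience and stratum make 5. Visit and treatment-by-visit add 2(T − 1).
- T = 12: 27 + 12 = 39 continuous; 27 + 312 − 1 = 338 categorical.
- T = 7: 17 + 7 = 24 continuous; 17 + 182 − 1 = 198 categorical.

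The 1 is subtracted because the 16–27/28–42 stratum is a function of the baseline levels and is fully aliased with them.

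**Effect on the treatment estimate.** The Week 12 comparison was simulated as a logistic model for one visit. The following are assumptions, not in the documents: baseline UAS7 normal with mean 29 and SD 7, truncated to 16–42; UAS7 = 0 rates, placebo/active, of 5/20%, 10/30% and 10/45%; N = 110 and 130.
- About 9 to 16 of some 26 observed levels had no variation in outcome.
- With categorical baseline the treatment log odds ratio was finite in 90–100% of runs. Not every infinite estimate comes from the coding: at 5% placebo response, the chance of no placebo responder among 55 is 0.95^55 = 6%.
- At 10/30% the true value is ln[(0.30/0.70)/(0.10/0.90)] = 1.35. The categorical model gave 1.61 to 1.72 in separate sets of runs (1.61/1.35 = 1.19; 1.72/1.35 = 1.27). At 10/45% it gave 2.55 against 2.00 (1.28). Over all scenarios the inflation was about 20–30%.
- The standard error was about 20–33% larger than with continuous baseline.
- With continuous baseline the median was close to the truth (1.34 against 1.35 at N = 130, 10/30%).

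The full repeated-measures model was not run. An unstructured covariance over 12 weeks would add 12 × 13/2 = 78 parameters.

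**The case against.** A reader might infer that the model cannot be estimated at all, that the check cannot be delivered, or that the repair would be made with unblinded data. None of these is supported. The coefficients that diverge belong to baseline levels; the treatment contrast stayed finite in nearly all simulated runs. Aliasing makes the stratum's own coefficient redundant but does not remove the treatment contrast. SAP 5.1 allows other methods to be considered before database lock and documented, and SAP 5.6 withholds the randomization code until lock.

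The better objection is that this is a wording slip which a competent programmer would correct. A second list makes sense only if baseline was to be treated differently from the first list, and the protocol ANCOVA and the neighbouring MMRM show how. That is probably right, and it limits the severity. It does not remove the point, because no code for this model overrides the sentence.

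Two further objections stand in part. The SAP says only baseline, so baseline UAS7 is inferred. The other reading, response status at baseline, does not rescue the text: every eligible subject has UAS7 of at least 16, so that term would be constant and drop out. And no confirmatory decision rests on this model, because the testing sequence uses the CMH result.

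**Conclusion.** The point holds as a minor specification error in a sensitivity analysis. Programmed as written, the model spends 182 to 312 parameters on baseline terms instead of 7 to 12 and makes the UAS7 stratum redundant. At Week 12 it would probably overstate the treatment log odds ratio by about 20–30%, with a larger standard error. Failure to converge is a risk, not an established result.

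The parameter counts assume that baseline means baseline UAS7 with 27 integer levels; prorated values would add levels. The size of the bias rests on the assumed baseline distribution and response rates and on a single-visit simulation.

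**What to change.** In SAP 6.9.2, replace the second list by: *and baseline UAS7 (or the baseline of the relevant score) and baseline-by-visit interaction as continuous covariates*. The stratum is then no longer aliased.

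Complete the sentence so that it says what the model will report: the odds ratio with its standard error, 95% confidence interval and p-value at named time points. It would help to state the link, the visits, the covariance structure and a convergence fallback in the same edit, and to add an output table, since no legible title in Appendix 2 covers this model.

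This is a short SAP amendment before database lock. It needs no new data and places no burden on patients.
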